### **6.3.3.3    Electrocardiogram (ECG)**

The incidence rates of treatment-emergent ECG abnormalities will be tabulated by treatment group. A descriptive analysis of continuous ECG parameters and their changes from baseline by visit and treatment group will also be presented.

Prolongations of QT interval will be summarized by visit and treatment group based on the PKS. At every time point the 90% Confidence Intervals (CI) for the mean change from baseline in QTcF will be calculated.

## **7.     Document history and changes in the planned statistical analysis**

### **7.1     Document history**

- Version 1.0
- Version 2.0
  - Added updates per the FDA Type C meeting held on 11/6/2019
  - Added definition of completer
  - Updated definition of baseline, treatment compliance calculation , and treatment duration calculation
  - Updated with latest SAS code
  - Included imputation rules for partially missing end dates for study medication

#### **7.1.1     Changes from the protocol**

None

## 9. Appendix

### 9.1 Pattern-mixture modeling approach

The main idea of this method was introduced by Little and Yau (1996) [20] and later refined by Ratitch and O'Kelly (2011) [21]. The Ratitch and O'Kelly (2011) approach suggests using sequential regression and multiple imputation methodology to impute missing values after a subject's discontinuation from the trial based on "as treated" model, using actual dose after drop-out if it is known, or based on some plausible assumptions if unknown. In most clinical trials, patients stop taking experimental medication after discontinuation. In this case, the "as treated" model for discontinued patients would be based on the idea that patients are taking a zero dose of the experimental treatment.

In this control-based pattern imputation, the intent is to make no direct use of observed data from the experimental treatment arm for estimating the imputation model. Hence, PROC MI is called in such a way that it builds its imputation model only on data from the control arm, while it imputes missing data in both control and experimental treatment arms using a single control-based imputation model. This is achieved with a sequence of calls to PROC MI.

The general procedure for control-based pattern imputation is the following:

- (a) Impute the non-monotone data with the MCMC method and store the result of this partial imputation. In this study, the non-monotone data would represent those patients that discontinued study treatment prematurely, but was able to comeback at a later visit for assessment (e.g., dropped out at week 2 and missed assessments for week 6, then came back and completed week 12 visit).
- (b) Next, impute the monotone data with control based pattern imputation. Here it implies that the patients who were in the treatment group and no longer received the treatment will assume the same conditional distribution as those in the control group. We start with imputing missing data at the first time-point that has some missing data (defined as time-point 1).
- (c) Repeat (b) for all other time-points sequentially. Patients whose missing values were imputed in the last call to PROC MI will be included in the input dataset for the next call to PROC MI. Thus data for time-point  $t$ , filled in during the last call, will be used for predictor variables in the next call to PROC MI (for time point  $t + 1$ ), which is consistent with the internal workings of a single call to PROC MI to impute all time-points automatically.

This procedure is illustrated below by the following example code:

```
proc mi data = DATAIN out = DATAIN_MONO n impute = 100 seed = 123;
  var SCORE_0 SCORE_1 SCORE_2 SCORE_3 SCORE_4 SCORE_5;
  mcmc chain = multiple impute = monotone;
run;

proc mi data=DATAIN_Mono out = DATAIN_REG_IMP1 seed=123 n impute=1;
  class Trt;
  monotone reg ;
```

```

mnar model( SCORE_1 SCORE_2 SCORE_3 SCORE_4 SCORE_5 / modelobs= (Trt='0'));
var SCORE_0 SCORE_1 SCORE_2 SCORE_3 SCORE_4 SCORE_5 ;
run;

```

where SCORE\_0 , SCORE\_1, SCORE\_2, SCORE\_3, SCORE\_4, SCORE\_5 represent KCCQ PLS scores at baseline and post-baseline visits week 2, 6, 12, 18 and 24.

The same procedure is then repeated until all time-points are imputed.

## 9.2 Tipping point analysis approach

We intend to perform multiple imputation analysis for a specified sequence of shift parameters, which only adjust the imputed values for observations in the treatment group (TRT=1). Multiple imputation will be done using SAS PROC MI under MNAR assumption using the following generic code:

```

proc mi data=PLS_data seed=19334 nimpute=1 out=PLS_mi;
  class Trt;
  monotone reg (/details);
  mnar model( SCORE_1 SCORE_2 SCORE_3 SCORE_4 SCORE_5 / modelobs= (Trt='0'))
    adjust (SCORE_1 SCORE_2 SCORE_3 SCORE_4 SCORE_5 /shift=sj adjustobs=(Trt='1'));
  var SCORE_0 SCORE_1 SCORE_2 SCORE_3 SCORE_4 SCORE_5;
run;

```

Each imputed observation (missing KCCQ PLS scores) will be modified according to the required delta shift. Assuming there is no penalty in KCCQ PLS score in the placebo group, then for those with missing outcomes in vericiguat treatment arm, we decrease the score gradually until a p-value of 0.025 or higher is produced (beyond the tipping point). The actual penalty (to 1 decimal place) that gives a p-value above and closest to 0.025 will then be identified.

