### 6.2.3.2 Supportive Analysis of the Primary Efficacy Variables

A tipping point analysis will be performed as the sensitivity analysis under missing not at random (MNAR) assumption. Based on the primary analysis model, we will vary assumptions about the missing outcomes to assess how severe departures from the control-based imputation model it can be to overturn the statistical significance conclusions. The procedure will impute the missing data with observations only from placebo arm, and adjust the imputed values for observations in the vericiguat treatment arm for a specified sequence of shift parameters. Multiple imputation will be done using SAS PROC MI under missing not at random (MNAR) assumption (Appendix 9.2).

Also, the same primary efficacy model will be repeated on PEAS (Section 5.1.4) as a supportive efficacy analysis.

In addition, the primary analysis model will be applied to all assessments post-baseline prior to study treatment discontinuation on FAS and PPS.

Furthermore, the same primary analysis model will be repeated under missing at random (MAR) assumption, which means no missing data imputations will be performed.

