### 6.2.5 Multiplicity adjustment

The study uses the graphical method of Maurer and Bretz [22] to provide strong multiplicity control across the primary KCCQ PLS hypotheses and the secondary 6 MWT hypotheses. The overall two-sided alpha level will be controlled at 0.05. The two primary hypotheses will be tested using the Bonferroni procedure, each at a splitted level of alpha 0.025. The two secondary hypotheses will be tested based on a parallel gatekeeping principle. As shown in Figure 6-1, if the test of both primary and secondary endpoints at one of the dose groups is significant at the alpha level of 0.025, the primary and secondary endpoint at the other dose group can be tested at the alpha level of 0.05, in an ordered manner. Figure 6-1 shows the  $\alpha$ -allocation for each hypothesis in the circle representing the hypothesis.

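### The tipping-point search stops at p = 0.025 for every dose, so a dose won only at the recycled 0.05 level is reported as tipped at zero shift

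*SAP*

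**What the plan says.** SAP 6.2.3.2 plans a tipping-point analysis as a sensitivity analysis of the primary endpoint. Its aim is to find how far the missing outcomes must depart from the control-based imputation model "to overturn the statistical significance conclusions".

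SAP 9.2 gives the rule. Imputed scores in the vericiguat arm are penalised step by step: "we decrease the score gradually until a p-value of 0.025 or higher is produced". The quantity reported is the penalty, to one decimal place, that "gives a p-value above and closest to 0.025 will then be identified". No other level is mentioned. The code is introduced as generic. It models missing values from Trt='0' and shifts only Trt='1'.

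SAP 6.2.5 sets the levels at which the conclusions are drawn. "The overall two-sided alpha level will be controlled at 0.05", and the two primary hypotheses start "each at a splitted level of alpha 0.025". If one dose is significant on both its primary and secondary endpoints at 0.025, then "the primary and secondary endpoint at the other dose group can be tested at the alpha level of 0.05, in an ordered manner". Protocol 10.3.1 describes the same recycling for a primary hypothesis that failed at first: the 0.025 attached to the winning dose is passed to it.

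**The concern.** A tipping-point analysis answers its question only if it stops at the level where the conclusion changes. In this design that level is not always 0.025. A dose that fails at 0.025 but is rejected at 0.05 after recycling is a significant result under the SAP, yet the search in SAP 9.2 treats it as lost from the start.

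The reported tipping point would be zero whatever the amount of missing data and however mild or harsh the shifts needed to reverse the finding. A reader of the study report would take that as a result with no robustness, when it is only a consequence of the stopping level. Choosing a different level after unblinding would make the sensitivity analysis post hoc.

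**Working it through.** **Inputs.** From protocol 10.4: 245 patients per arm, 5 points on KCCQ PLS for both doses, SD 21; 6MWT SD 80 m, with power quoted for 30 m and 22.3 m. From SAP 6.2.5: 0.025 per dose initially, and 0.025 + 0.025 = 0.05 after recycling. Assumed, because the documents give no figure: PLS–6MWT correlation of 0 to 0.5, and the share of week-24 scores that are imputed.

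**Step 1: reproduce the plan's own power.**
- SE of a PLS difference = 21 × √(2/245) = 1.897. Non-centrality = 5/1.897 = 2.635. Critical z at two-sided 0.025 = 2.241.
- Marginal power = Φ(2.635 − 2.241) = 65.3% (stated: 65%).
- Power for at least one dose, bivariate normal with correlation 0.5 from the shared placebo arm = 80.6% (stated: 80%).
- 6MWT: SE = 80 × √(2/245) = 7.228 m. Power at 0.025 is 97.2% for 30 m (stated: 97%) and 80.1% for 22.3 m (stated: 80%).

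So 0.025 is the starting level per hypothesis, and the model below matches the plan.

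**Step 2: where a recycled win lies.** A dose won only at 0.05 has z between 1.960 and 2.241. The observed difference is then between 1.960 × 1.897 = 3.72 and 2.241 × 1.897 = 4.25 points. A shift of zero is the primary control-based imputation itself, so p is already at or above 0.025 and the search stops at once. The only slack is Monte Carlo noise: the example code uses a different seed in SAP 9.1 and 9.2.

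**Step 3: how often.** The graph was simulated (2 to 4 million draws per setting) with four correlated z-statistics: correlation 0.5 between doses, and 0 to 0.5 between PLS and 6MWT. PLS is 5 points for both doses throughout.

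| True 6MWT effect, both doses | One dose won only by recycling |
|---|---|
| 30 m | 10.6–10.8% of trials |
| 22.3 m | 8.7–9.4% |
| 15 m | 4.7–5.5% |
| 10 m | 2.1–2.4% |
| 0 m | about 0.1% |

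At 22.3–30 m this is about 11–13% of the trials in which at least one dose is won.

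**Step 4: what is lost.** Take p = 0.03: z = 2.170 and the difference is 4.12 points. The mean can fall by (2.170 − 1.960) × 1.897 = 0.40 points before p reaches 0.05. The shift per imputed score is 0.40 divided by the imputed share:
- 5% imputed: about 8.0 points
- 10% imputed: about 4.0 points
- 20% imputed: about 2.0 points

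At p = 0.04 the corresponding shifts are about 3.6, 1.8 and 0.9 points. The rule as written reports 0 in every case. This approximation holds the SE fixed and ignores carry-over of shifts between visits.

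**Step 5: doses that pass at 0.025.** If both doses pass at 0.025 on PLS and the other dose also wins its 6MWT at 0.025, this dose would keep its rejection up to p = 0.05. Stopping at 0.025 then gives a tipping point that is too small, though not zero. At least one dose is in this position in about 46–50% of trials at 22.3–30 m.

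**The case against.** The analysis is supportive, and 0.025 is the level at which each primary hypothesis is first tested, so it can be defended as a conservative choice. Dropout is planned as negligible (protocol 10.4) and missing data as few (protocol 11.4). SAP 9.2 already runs a sequence of shifts, so a 0.05 crossing could be read from the same procedure. All of this stands and limits the weight of the point. It does not remove it: the stated aim is to find what overturns the conclusion, and for a recycled win the rule cannot do so.

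The frequency is also open to challenge. Recycling needs a 6MWT win, the correlation is assumed, and 22.3 m is the effect detectable with 80% power rather than an expected effect. The 9–11% is the upper part of a range that reaches down to about 0.1%.

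A reader might infer three stronger things that the documents do not support:
- **That a false-positive risk follows.** It does not. The rule plays no part in the primary test or the success criterion, and its error understates robustness.
- **That both doses in an affected trial get a wrong tipping point.** Only the recycled dose does. The dose that won first was tested at 0.025, and 0.025 is its correct stop.
- **That the second active arm is never penalised, because only Trt='1' is shifted.** That would follow from coding the arms 0/1/2, which appears nowhere. Trt is undefined and is not the three-level variable of the primary model. One two-arm run per dose fits the text, and the printed code would then work. Pooling both doses as 1 would instead shift them together. This is missing detail, not a demonstrated programming error.

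**Conclusion.** The point holds for the stopping level. SAP 9.2 fixes 0.025, SAP 6.2.5 and protocol 10.3.1 allow a dose to be won at 0.05, and nothing links the two. For a dose won only by recycling, the tipping point is zero by construction, apart from Monte Carlo noise.

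Given 5 points on PLS for both doses and the assumed correlation range, the chance of this depends mainly on the true 6MWT effect, as tabulated above: about one trial in ten at the effects used in the power statement, and almost never without a 6MWT effect. The shift that goes unreported depends on the share of imputed scores, which the documents do not give.

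This is a minor correction to a sensitivity analysis. The Trt coding is a request for clarification only.

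**What to change.** In SAP 9.2, replace the fixed level with a rule per dose: stop at the p-value at which that dose's rejection would be lost under the graph, with the other dose's results held fixed. That is 0.05 if the other dose has won both its primary and its secondary hypothesis at 0.025, and 0.025 otherwise. Tying the stop only to the level at which the dose happened to be rejected would not be enough, because it would miss the doses in step 5.

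As a clarification, state how Trt is coded and that the code is run separately for each dose against placebo, shifting only that dose's imputed values. Per-dose runs are also what make it meaningful to hold the other dose's results fixed.

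The cost is about two sentences and one code parameter, settled before unblinding. Data collection, sample size and the primary analysis do not change.

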## 9.3 Region Definition

CNTYGR1 Pooled Country/Geographic Region 1	COUNTRY Country
Americas	ARGENTINA
Americas	CANADA
Americas	COLOMBIA
Americas	UNITED STATES
Asia/Pacific	JAPAN

# Statistical Analysis Plan

Protocol No.: **BAY 1021189 /19334**

Page: 40 of 40

Asia/Pacific	MALAYSIA
Asia/Pacific	SINGAPORE
Asia/Pacific	TAIWAN (PROVINCE OF CHINA)
Europe (incl. Israel and South Africa)	AUSTRIA
Europe (incl. Israel and South Africa)	BELGIUM
Europe (incl. Israel and South Africa)	BULGARIA
Europe (incl. Israel and South Africa)	GERMANY
Europe (incl. Israel and South Africa)	SPAIN
Europe (incl. Israel and South Africa)	GREECE
Europe (incl. Israel and South Africa)	HUNGARY
Europe (incl. Israel and South Africa)	ISRAEL
Europe (incl. Israel and South Africa)	ITALY
Europe (incl. Israel and South Africa)	POLAND
Europe (incl. Israel and South Africa)	PORTUGAL
Europe (incl. Israel and South Africa)	RUSSIAN FEDERATION
Europe (incl. Israel and South Africa)	SOUTH AFRICA
